### **5.3.1.2 Collection and Handling of In Vivo Pharmacodynamic Biomarker and Optional Samples for Exploratory Research and Validation Studies**

#### **5.3.1.2.1 In Vivo Pharmacodynamic Biomarker Samples**

Blood samples will be collected at the visits indicated in [Appendix D](#) and [Appendix F](#) and will be utilized to assess effects of upadacitinib inhibition on certain lymphocyte subsets, including but not limited to T (CD4+ and CD8+) cells, B (CD19+) cells, natural killer (NK) cells, and natural killer-T (NKT) cells.

The samples should be labeled and shipped as outlined in the study-specific laboratory manual.

#### **5.3.1.2.2 Optional Samples for Exploratory Research and Validation Studies**

In Period 1, subjects will have the option to provide samples for exploratory research and validation studies. Subjects may still participate in the study even if they decide not to participate in this optional exploratory research/validation study.

Exploratory research can help to improve our understanding of how individuals respond to drugs and our ability to predict which subjects would benefit from receiving specific therapies. In addition, exploratory research may help to improve our understanding of

how to diagnose and assess/monitor RA by assessing associations between disease characteristics, outcomes data, and biomarkers of interest.

Validation studies, including those related to the development of potential in vitro diagnostic tests, may be carried out retrospectively in order to assess associations between events of interest (i.e., efficacy and/or safety events) and candidate biomarkers.

AbbVie (or people or companies working with AbbVie) will store the biomarker exploratory research/validation studies samples in a secure storage space with adequate measures to protect confidentiality. The samples will be retained while research on upadacitinib (or drugs of this class) or RA and related conditions continues, but for no longer than 20 years after the completion of Period 1.

#### **DNA Samples for Pharmacogenetic or Epigenetic Analyses**

Whole blood samples for DNA isolation will be collected at the visits indicated in [Appendix E](#) from each subject who consents to provide samples for exploratory/validation research. The procedure for obtaining and documenting informed consent is discussed in Section 9.3.

Samples will be shipped frozen to AbbVie or a designated laboratory for DNA extraction and/or long-term storage or analyses. Instructions for the preparation and shipment of the pharmacogenetic and/or epigenetic research samples will be provided in a laboratory manual.

#### **RNA Samples for Transcriptomic and/or Epigenetic Analyses**

Whole blood samples for RNA isolation will be collected at the visits indicated in [Appendix E](#) from each subject who consents to provide samples for exploratory/validation research. The procedure for obtaining and documenting informed consent is discussed in Section 9.3.

Samples will be shipped to AbbVie or a designated laboratory for RNA extraction and/or long-term storage or analyses. Instructions for the preparation and shipment of the samples will be provided in a laboratory manual.

**Serum and Plasma Samples for Systemic Analyses, Including but Not Limited to Proteomic and Metabolomic**

Serum and plasma samples will be collected at the visits indicated in [Appendix E](#) from each subject who consents to provide samples for exploratory/validation research. The procedure for obtaining and documenting informed consent is discussed in Section 9.3.

Samples will be shipped to AbbVie or a designated laboratory for long-term storage and/or analyses. Instructions for the preparation and shipment of the samples will be provided in a laboratory manual.

**5.3.2 Drug Concentration Measurements**

**5.3.2.1 Collection of Samples for Analysis**

Blood samples for assay of upadacitinib and possibly other concomitant medications will be collected as follows:

- Weeks 1 and 2 prior to dosing;
- Weeks 4, 8, 12, 16, 20, and 24/PD at any time during the visit.

On Week 1 and Week 2 visit days, if possible, subjects should take the study drug dose at the clinic after collecting the PK blood sample, except if the subjects regularly take the study drug dose at night. Those subjects who regularly take the study drug dose at night should continue to take study drug according to their normal schedule. For all other visits, subjects can take the study drug dose on visit days at their regular schedule and not necessarily at the clinic.

The date and accurate time of the PK sample collection will be recorded on the lab requisition form. The date and accurate time of the last two study drug doses will be recorded on the eCRF to the nearest minute.

Refer to the study specific laboratory manual for detailed instructions on sample collection, processing, and shipment.

### **5.3.2.2 Measurement Methods**

Plasma concentrations of upadacitinib will be determined by the Drug Analysis Department at AbbVie using a validated liquid chromatography/mass spectrometry method.

### **5.3.3 Efficacy Variables**

#### **5.3.3.1 Period 1 Variables**

##### **5.3.3.1.1 Primary Variable**

The primary endpoint is the proportion of subjects achieving ACR20 response (US/FDA regulatory purposes) or the proportion of subjects achieving LDA (EU/EMA regulatory purposes) at Week 12. Analyses will be conducted separately for US/FDA regulatory purposes and EU/EMA regulatory purposes; for each set of analysis, only one primary endpoint is specified.

ACR20 response rate will be determined based on 20% or greater improvement in TJC and SJC and  $\geq 3$  of the 5 measures of Patient's Assessment of Pain (VAS), Patient's Global Assessment of Disease Activity (VAS), Physician's Global Assessment of Disease Activity (VAS), HAQ-DI, or hsCRP.

LDA is defined as DAS28 (CRP)  $\leq 3.2$ . DAS28 (CRP) score will be determined based on a continuous scale of combined measures of TJC, SJC, Patient's Global Assessment of Disease Activity (PtGA) (in mm), and hsCRP (in mg/L) at Week 12.

$$\text{DAS28 (CRP)} = 0.56 \times \sqrt{(\text{TJC28}^*)} + 0.28 \times \sqrt{(\text{SJC28}^{**})} + 0.36 \times \ln(\text{hsCRP}^{\&} + 1) + 0.014 \times \text{PtGA}^{\gg} + 0.96$$

\* TJC28 refers to the Subject's total Tender Joint Count out of the provided 28 evaluated joints.

\*\* SJC28 refers to the Subject's total Swollen Joint Count out of the provided 28 evaluated joints.

& hsCRP refers to the high-sensitivity c-reactive protein lab value. hsCRP unit in the DAS28 (CRP) equation is expressed as mg/L.

» PtGA refers to the Patient's Global Assessment of Disease Activity.  
where  $\sqrt{\phantom{x}}$  is square root and  $\ln$  is natural log.

### 5.3.3.1.2 Key Secondary Variables

Ranked key secondary endpoints (at Week 12) for US/FDA regulatory purposes are:

1. Change from baseline in DAS28 (CRP);
2. Change from baseline in HAQ-DI;
3. LDA as measured by DAS28 (CRP);
4. Change from baseline in SF-36 Physical Component Score (PCS);

Ranked key secondary endpoints in Period 1 (at Week 12) for EU/EMA regulatory purposes are:

1. Change from baseline in DAS28 (CRP);
2. ACR20 response rate;
3. Change from baseline in HAQ-DI;
4. Change from baseline in SF-36 Physical Component Score (PCS);

Other key secondary endpoints (at Week 12) for both US/FDA and EU/EMA regulatory purposes are:

1. ACR50 response rate;
2. ACR70 response rate;

3. ACR20 response rate at Week 1.

ACR20/50/70 response rates will be determined based on 20%/50%/70% or greater improvement in TJC and SJC and  $\geq 3$  of the 5 measures of Patient's Assessment of Pain (VAS), Patient's Global Assessment of Disease Activity (VAS), Physician's Global Assessment of Disease Activity (VAS), HAQ-DI, or hsCRP.

**5.3.3.1.3 Additional Variables**

Additional endpoints at all visits are:

- Change from baseline in individual components of ACR response;
- ACR20/50/70 response rates;
- Change from baseline in DAS28 (CRP) and DAS28 (erythrocyte sedimentation rate [ESR]);
- Change from baseline in CDAI and SDAI;
- Change from baseline in morning stiffness;
- Proportion of subjects achieving change from baseline in HAQ-DI  $\leq -0.3$ ;
- Proportion of subjects achieving LDA and proportion of subjects achieving CR based on DAS28 (CRP), DAS28 (ESR), Simplified Disease Activity Index (SDAI), and CDAI criteria (see below);
- ACR/EULAR Boolean remission;

---

	DAS28 (CRP) and DAS28 (ESR)	SDAI	CDAI
LDA	$\leq 3.2$	$\leq 11.0$	$\leq 10$
CR	$< 2.6$	$\leq 3.3$	$\leq 2.8$

---

Additional endpoints (at Weeks 4, 12, and 24) are:

- Change from baseline in EQ-5D-5L;
- Change from baseline in ISI (sleep);
- Change from baseline in SF-36.

### **5.3.3.2 Period 2 Variables**

Assessments to evaluate efficacy of treatment in Period 2 will be analyzed for the following measures at Weeks 36, 48, every 12 weeks through Week 240, and Week 260/PD:

- ACR20/50/70 response rates;
- Change from baseline in individual ACR components;
- Change from baseline in DAS28 (CRP);
- Change from baseline in DAS28 (ESR);
- Change from baseline in morning stiffness;
- Proportion of subjects achieving change from baseline in HAQ-DI  $\leq -0.3$ ;
- Proportion of subjects achieving LDA and proportion of subjects achieving CR based on DAS28 (CRP), DAS28 (ESR), SDAI, and CDAI criteria (as defined for Period 1);
- Concomitant corticosteroid use.

Assessments to evaluate efficacy of treatment in Period 2 will be analyzed for the following measures at Week 48 only:

- Change from baseline in EQ-5D-5L;
- Change from baseline in ISI (sleep);
- Change from baseline in SF-36.

### **5.3.4 Safety Variables**

Safety evaluations include adverse event monitoring, physical examinations, vital sign measurements, ECG, and clinical laboratory testing (hematology, chemistry, and urinalysis) as a measure of safety and tolerability for the entire study duration.

### **5.3.5 Pharmacokinetic Variables**

Plasma upadacitinib concentrations will be obtained at the times indicated in [Appendix D](#). A non-linear mixed-effects modeling approach will be used to estimate the population central values and the empirical Bayesian estimates of the individual values of upadacitinib oral clearance (CL/F) and volume of distribution (V/F). Additional parameters may be estimated if useful in the interpretation of the data.

### **5.3.6 In Vivo Pharmacodynamic Biomarker Samples and Exploratory Research Variables and Validation Studies**

#### **5.3.6.1 In Vivo Pharmacodynamic Biomarker Samples**

Blood samples will be collected to assess the effects of upadacitinib inhibition on lymphocyte subsets including but not limited to: T (CD4+ and CD8+) cells, B (CD19+) cells, NK cells, and NKT cells.

#### **5.3.6.2 Exploratory Research Variables and Validation Studies**

Optional samples may be collected to conduct exploratory investigations into known and novel biomarkers. The types of biomarkers to be analyzed may include, but are not limited to nucleic acids, proteins, lipids, or metabolites.

Biomarker assessments may be used to assess and generate prognostic, predictive, pharmacodynamic, or surrogate biomarker signatures. These assessments may be explored in the context of RA or related conditions and/or upadacitinib or drugs of similar classes. The results from these analyses are exploratory in nature and may not be included with the clinical study report (CSR).

The samples may also be used to develop new therapies, research methods or technologies. In addition, samples from this study may be stored for future use. Samples may then be used to validate putative biomarker signatures obtained from a prospective study, leading to the development of diagnostic tests.

## **5.4 Removal of Subjects from Therapy or Assessment**

### **5.4.1 Discontinuation of Individual Subjects**

Subjects can request to be discontinued from participating in the study at any time for any reason including but not limited to disease progression or lack of response to treatment. The Investigator may discontinue any subject's participation for any reason, including an AE, safety concerns, lack of efficacy, or failure to comply with the protocol. See Section 6.1.7 for toxicity management criteria.

Subjects will have study drug discontinued immediately if any of the following occur:

- Clinically significant abnormal laboratory results or AEs, which rule out safe continuation of the study drug, as determined by the Investigator or the AbbVie Therapeutic Area Medical Director.
- Serious infections (e.g., sepsis) which cannot be adequately controlled within 2 weeks by anti-infective treatment or would put the subject at risk for continued participation in the trial as determined by the Investigator.
- The Investigator believes it is in the best interest of the subject.
- The subject requests withdrawal from the study.
- Inclusion or exclusion criteria violation was noted after the subject started study drug, when continuation of the study drug would place the subject at risk as determined by the AbbVie Therapeutic Area Medical Director.
- Introduction of prohibited medications or dosages when continuation of the study drug would place the subject at risk, as determined by the AbbVie Therapeutic Area Medical Director.
- Subject is non-compliant with TB prophylaxis (if applicable) or develops active TB at any time during the study.
- The subject becomes pregnant while on study drug.
- Malignancy, except for localized NMSC or carcinoma in-situ of the cervix.
- Subject is significantly non-compliant with study procedures which would put the subject at risk for continued participation in the trial as determined by the Investigator or the AbbVie Therapeutic Area Medical Director.

- Subject develops a gastrointestinal perforation (other than due to appendicitis or mechanical injury).
- Starting at Week 24 and thereafter, subject fails to show at least 20% improvement in both TJC and SJC compared to baseline at 2 consecutive visits, despite optimization of background RA therapies.
- Confirmed diagnosis of deep vein thrombosis, pulmonary embolus or non-cardiac, non-neurologic arterial thrombosis.

In order to minimize missing data for efficacy and safety assessments, subjects who prematurely discontinue study drug treatment should complete a Premature Discontinuation visit (PD visit) as soon as possible, preferably within 2 weeks. Afterwards, subjects should continue to be followed for all regularly scheduled visits, unless they have decided to discontinue the study participation entirely (withdrawal informed consent). Subjects should be advised on the continued scientific importance of their data even if they discontinue treatment with study drug early.

If a subject prematurely discontinues study drug treatment and study participation (withdrawal of informed consent), the procedures outlined for the Premature Discontinuation visit (PD visit) should be completed as soon as possible, preferably within 2 weeks of study drug discontinuation. In addition, if subject is willing, a 30-day follow-up phone call (or visit) after the last dose of study drug may be completed to ensure all treatment emergent AEs/SAEs have been resolved or the occurrence of any new AEs/SAEs. Subjects who discontinue the study prematurely after randomization will not be replaced.

All attempts must be made to determine the date of the last study drug dose and the primary reason for discontinuation of study drug or study participation. The information will be recorded on the appropriate eCRF page. However, these procedures should not interfere with the initiation of any new treatments or therapeutic modalities that the Investigator feels are necessary to treat the subject's condition. Following discontinuation of study drug, the subject will be treated in accordance with the Investigator's best clinical judgment irrespective of whether the subject decides to continue participation in the study.

During the COVID 19 pandemic, it has been necessary to employ mitigation strategies to enable the investigator to ensure subject safety and continuity of care.

During a state of emergency or pandemic situation like COVID-19, the investigator should contact the sponsor medical contact before discontinuing a subject from the study or study drug for a reason other than "planned per protocol," to ensure all acceptable mitigation steps have been explored.

Additional local requirements may apply. Refer to [Appendix C](#) for local requirements for France.

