Added provision allowing the urine pregnancy test to be performed at a local laboratory or at home. Removed the reference to contraception requirements for male subjects with a partner of childbearing potential for consistency with Section 5.2.4 "Contraception Recommendations."

- Clinical Laboratory Tests

Added provision allowing the laboratory testing at an alternate local facility, in the event that a state of emergency or pandemic prevents the subject from performing the central laboratory tests and added the requirements to allow the study drug dispensation when laboratory tests are performed at a local laboratory.

- Study Drug Dispensing, Dosing and Compliance

Added provision allowing Direct-to-Patient (DTP) shipment of study drug and study ancillaries due to state of emergency or pandemic situations.

- New Section: Optional Home Healthcare Service Due to State of Emergency or Pandemic Situation like COVID-19

Added home healthcare visits as an option in case a study visit on site cannot be performed due to state of emergency or pandemic-related reasons.

***Rationale:*** *To modify study visits and protocol-specific procedures impacted by the COVID-19 or any pandemic/state of emergency as necessary, to ensure the safety of subjects/site staff and study continuation including alternative locations for data collection, as permitted by IRB/IEC.*

- Update Section 5.4.1, Discontinuation of Individual Subjects

***Rationale:*** *Revised to clarify that subjects will have to discontinue study drug treatment immediately if they develop a gastrointestinal perforation with the exception of appendicitis or mechanical injury to be consistent with the Section 6.1.7 "Toxicity Management."*

*Clarified that the state of emergency and pandemic-related restrictions may allow mitigation strategies to ensure subject safety and continuity of care as an alternative to study discontinuation/study drug discontinuation and that the AbbVie TA MD should be contacted before discontinuing a subject to ensure all acceptable mitigation steps have been explored.*

- Update Section 5.5.1, Treatments Administered

***Rationale:*** *Added specifications in order to provide the study drug through DTP shipment in the event pandemic situation like COVID-19 or state of*

*emergency prevent the study drug dispensation to the subject onsite, if permitted by local regulations.*

- Update Section 6.1.1.3, Adverse Events of Special Interest  

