### **6.1.1.3 Adverse Events of Special Interest**

The following AEs of special interest will be monitored during the study (see detailed toxicity management in Section 6.1.7):

- Serious infections
- Opportunistic infections
- Herpes zoster
- Active tuberculosis
- Malignancy (all types)
- Adjudicated gastrointestinal perforations

- Adjudicated cardiovascular events (e.g., major adverse cardiovascular event [MACE])
- Anemia
- Neutropenia
- Lymphopenia
- Increased serum creatinine and renal dysfunction
- Hepatic events and increased hepatic transaminases
- Elevated creatine phosphokinase (CPK)
- Adjudicated embolic and thrombotic events (non-cardiac, non-CNS).

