**Thrombosis Events:** Subjects who develop symptoms of thrombosis should be promptly evaluated and treated appropriately. If the diagnosis of deep vein thrombosis, pulmonary embolus or non-cardiac, non-neurologic arterial thrombosis is confirmed, the subject must be discontinued from study drug.

**Malignancy:** Subjects who develop malignancy other than NMSC or carcinoma in situ of the cervix must be discontinued from study drug. Information including histopathological results should be queried for the confirmation of the diagnosis. Periodic skin examination is recommended for subjects who are at increased risk for skin cancer.

**ECG Abnormality:** Subjects must be discontinued from study drug for an ECG change considered clinically significant and with reasonable possibility of relationship to study drug OR a confirmed absolute QTcF value > 500 msec.

**Management of Select Laboratory Abnormalities:** For any given laboratory abnormality, the Investigator should assess the subject, apply the standard of care for medical evaluation and treatment following any local guidelines. Specific toxicity management guidelines for abnormal laboratory values are described in [Table 4](#), and may require an appropriate supplemental eCRF to be completed. All abnormal laboratory tests that are considered clinically significant by the Investigator will be followed to a satisfactory resolution. If a repeat test is required per [Table 4](#), the repeat testing must occur as soon as possible.

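### Outside France, non-localized NMSC is a mandatory stop in Protocol 5.4.1 but falls within the exemption in 6.1.7, which omits the word 'localized'

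*Protocol*

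**What the plan says.** Section 5.4.1 (Discontinuation of Individual Subjects) gives a list of events, any one of which requires immediate discontinuation of study drug. The cancer item is "Malignancy, except for localized NMSC or carcinoma in-situ of the cervix".

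Section 6.1.7 (Toxicity Management), in its malignancy paragraph, says "Subjects who develop malignancy other than NMSC or carcinoma in situ of the cervix must be discontinued from study drug". It adds: "Information including histopathological results should be queried for the confirmation of the diagnosis".

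The two sections are linked. Section 5.4.1 directs the reader onward: "See Section 6.1.7 for toxicity management criteria". Section 6.1.1.3, whose list includes malignancy of all types, does the same: "The following AEs of special interest will be monitored during the study (see detailed toxicity management in Section 6.1.7". The abbreviation list expands NMSC as non-melanoma skin cancer and attaches no stage to it.

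Appendix C replaces both sections for France. There, each section stops study drug for any malignancy, with no NMSC exemption. The Appendix C entries for Canada, Germany and Korea concern contraception and leave the malignancy rule alone.

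**The concern.** The same stopping rule appears twice with different scope. Under 5.4.1 the exemption covers localized NMSC only, so NMSC that has spread is a mandatory stop. Under 6.1.7 the exemption covers all NMSC. The text does not say which section governs.

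The stake is patient safety at site level. A site handling a skin cancer is sent to 6.1.7 by two separate cross-references. If it works from that section alone, it finds no explicit stop for non-localized NMSC, and stopping then depends on an individual judgment instead of the stated rule.

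There is a smaller consequence for records. SAP Section 6.4 counts as a deviation a subject who met a withdrawal criterion and was not withdrawn. A subject with non-localized NMSC kept on drug would meet that definition under 5.4.1 but not under the malignancy paragraph of 6.1.7.

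**Working it through.** No arithmetic applies. The check is to take each type of malignancy and read off what each current text requires.

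| Case | Section 5.4.1 | Section 6.1.7, malignancy paragraph | Agree? |
|---|---|---|---|
| Localized NMSC | Exempt | Exempt | Yes |
| Non-localized NMSC | Mandatory stop | Exempt | **No** |
| Carcinoma in situ of the cervix | Exempt | Exempt | Yes |
| Any other malignancy | Mandatory stop | Mandatory stop | Yes |
| Any malignancy, France (Appendix C) | Mandatory stop | Mandatory stop | Yes |

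The reasoning for the one discordant row:

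1. The exception in 5.4.1 attaches 'localized' to NMSC. NMSC that is not localized is outside the exception, so the immediate-stop list applies.
2. The exception in 6.1.7 names NMSC without qualification, and the abbreviation list supplies none. NMSC at any stage is inside the exception, so this paragraph does not require a stop.
3. Both are current protocol text. Neither is an entry in the summary of changes.

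On how often the discordant case might arise, the documents offer little. The Introduction (Section 3.0) reports one upadacitinib subject with NMSC (basal cell and squamous cell carcinoma) in the two Phase 2 trials, total N = 575, and does not say whether the disease was localized. No rate for non-localized NMSC appears anywhere, so no expected count can be derived.

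**The case against.** The strongest reply is that the two sections do not conflict in operation. Each gives a condition sufficient for stopping, and 6.1.7 never says the drug may continue in NMSC. A site that follows the whole protocol has one answer, which is to stop under 5.4.1, the section dedicated to discontinuation. This is correct, and it is why the point is minor. What remains is that one statement of a mandatory rule is incomplete, in the section to which sites are sent for management of the event.

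The second reply is that other safeguards cover the gap. Section 5.4.1 also stops the drug for adverse events "which rule out safe continuation of the study drug, as determined by the Investigator or the AbbVie Therapeutic Area Medical Director", and where "The Investigator believes it is in the best interest of the subject". Section 6.1.7 has histopathology queried. These stand and reduce the consequence. They are not equivalent to the explicit rule: the first two need a case-by-case decision, and the query confirms a diagnosis without requiring a stop.

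Third, the protocol uses 'localized' loosely. Exclusion criterion 11 attaches the word to cervical carcinoma in situ and not to NMSC, so one may doubt that 5.4.1 meant to create a separate category. The doubt is fair as to drafting intent. But criterion 11 governs entry and changes neither stopping rule.

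Finally, the summary of changes shows the sponsor reconciling these sections on gastrointestinal perforation in this amendment, by revising 5.4.1 "with the exception of appendicitis or mechanical injury to be consistent with the Section 6.1.7". There 5.4.1 was moved to match 6.1.7, and following that direction here would delete 'localized' from 5.4.1. The precedent therefore supports aligning the sections but does not settle the direction.

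**Conclusion.** The inconsistency is real and holds as stated: one qualifier, present in 5.4.1 and absent from 6.1.7, affecting one category of event (non-localized NMSC) outside France. Severity is minor.

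The conclusion rests on reading NMSC in 6.1.7 as the abbreviation list defines it, without a stage limit, and on the absence of any statement that one section overrides the other. The practical risk further assumes a site that acts on 6.1.7 without consulting 5.4.1. How often that would coincide with non-localized NMSC is unknown.

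Power, type I error, the efficacy analyses and data collection are unaffected. SAP Section 11.1 records that the primary analysis and Period 1 reporting are complete, so a correction acts only on the continuing conduct of Period 2.

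**What to change.** In the opening sentence of the malignancy paragraph of Section 6.1.7, insert 'localized' before NMSC. Leave 5.4.1 and the French text in Appendix C as they are.

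This direction is preferred because it keeps the stricter obligation already in 5.4.1. Deleting the word from 5.4.1 would also align the two sections, but by loosening a safety rule.

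The cost is one word in the next amendment and, until then, a short memo to sites stating that non-localized NMSC requires study drug to be stopped. No change to the case report forms or the SAP is needed. The edit does not define 'localized', which 5.4.1 also leaves undefined, so the boundary would still rest on clinical judgment.
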